Storage, dispensing and return

The AGE reader SU will be stored securely, in a locked room, or locked cupboard or cabinet. Access to the medical device will be limited to the study staff and investigators.

Placebo

No placebo products will be used in the present project.

Known Side Effects

The AGE-Reader has been extensively tested in thousands of adults for several years without any adverse effects. The AGE Reader has CE approval (2085393CE01) to be used as a medical device and thus has passed the rigid safety standard. The amount of ultraviolet light exposure is actually far below the safety limits.

Reference source:

AGE reader. Cardiovascular risk assessment. <http://www.diagnoptics.com/age-reader/>
[Accessed on 12th May, 2016]

TRIAL / STUDY DESIGN

TRIAL / STUDY CONFIGURATION

Studies 1 and 2 will be single-centre.

Study 1: longitudinal/prospective.

Study 2: observational non-randomized proof of principle study where malnourished dialysis participants will receive a dietitian supervised intensive nutritional support.

Primary endpoints

Study 1:

1. Changes in SAF levels after 12 months of follow-up.
2. One-year survival.

Study 2: changes in SAF levels after 6 months of a dietetic intervention (i.e. intensive nutritional support).

Secondary endpoints

Study 1:

- Factors associated with the accumulation of AGE.
- Association of SAF levels with morbidity, biochemical variables (haemoglobin, haemoglobin A1C (HbA1C), urea, creatinine, potassium, phosphate, calcium, sodium, albumin, total proteins, cholesterol, triglycerides, and intact parathyroid hormone), visual function, circulating AGE levels (carboxymethyl lysine [CML] and pentosidine), inflammatory biomarkers (tumour necrosis factor- α [TNF- α], interleukin 6 [IL-6], C reactive protein [CRP] and others) health-related quality of life and nutritional status (energy, protein and fat intake, dietary AGE intake, anthropometry and subjective global assessment [SGA]).

Study 2:

- Association of SAF levels with morbidity, biochemical variables (haemoglobin, HbA1C, urea, creatinine, potassium, phosphate, calcium, sodium, albumin, total proteins, cholesterol, triglycerides, and intact parathyroid hormone), visual function, circulating AGE levels (CML and pentosidine), inflammatory biomarkers (TNF- α , IL-6, CRP and others) health-related quality of life and nutritional status (energy, protein and fat intake, dietary AGE intake, anthropometry and SGA).

Safety endpoints

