- There will not be any safety endpoints for these studies.

Stopping rules and discontinuation

Participant Withdrawal

Participants will be withdrawn from the study if they withdraw their consent at any time. Participants may be withdrawn from the study at the discretion of the Investigator. Participants will be made aware that withdrawal will not affect their future care. Participants who withdraw will be asked for permission to retain data already collected for use in the final analysis.

If participants fail to attend for their study visits, a member of the research team will try to contact them by telephone within 24 hours of their appointment and by written correspondence within a week of the missed appointment. Multiple attempts at contact will be made by the research team over a period of a month before stating that a participant has been lost to follow-up.

Participants will be withdrawn from the study if they:

- Withdraw their consent at any point.
- Become pregnant.
- Decline to comply with the dietetic intervention (Study 2 only).

Criteria for terminating the study

Study 1 is observational and will therefore only be terminated if it becomes clear that for unforeseen reasons the study is not feasible.

The intervention in Study 2 is not expected to be associated with any adverse effects. Study 2 will therefore only be terminated if it becomes clear that for unforeseen reasons the study is not feasible.

RANDOMIZATION AND BLINDING

Maintenance of randomization codes and procedures for breaking code

TRIAL/STUDY MANAGEMENT

The Chief Investigator (CI; [name]) has overall responsibility for the study and shall oversee all study management. The data custodian will be the CI.

The study will be coordinated from the University of Nottingham campus at the Royal Derby Hospital. Data will be collected at the Renal Unit of the Department of Nephrology at the Royal Derby Hospital (Derby Teaching Hospitals NHS Foundation Trust) and stored at the University of Nottingham.

[name] (PhD student), [name] and [name] are responsible for study planning, recruitment, consenting, data collection, handling and interpretation.

DURATION OF THE TRIAL / STUDY AND PARTICIPANT INVOLVEMENT

Study Duration:

Study 1:

Participant recruitment will begin on June 2016 with an anticipated recruitment period of 14 months. Therefore, all baseline data and measurements will be collected and performed between June 2016 and August 2017.

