The Study 1 (prospective/longitudinal) involves SAF measurements and visual function, nutritional and quality of life assessments during one year of follow-up. Therefore, there is no need for an assessment of participant compliance with the study protocol. Should the participant not complete the study day, this will be classified as a withdrawal rather than non-compliance (see Section **Participant Withdrawal**).

Compliance with the intervention of Study 2 will be evaluated by means of three 24-h dietary recalls every month (1 dialysis day, 1 non-dialysis day and 1 weekend day for the HD participants and 2 weekdays and 1 weekend day for the PD participants).

Criteria for terminating trial

Study 1 is observational and will therefore only be terminated if it becomes clear that for unforeseen reasons the study is not feasible.

The intervention in Study 2 is not expected to be associated with any adverse effects. Study 2 will therefore only be terminated if it becomes clear that for unforeseen reasons the study is not feasible.

TRANSPORT AND STORAGE OF THE TISSUES

Blood samples (10 mL) will be collected at intervals as described and centrifuged. At least 2 mL of serum and 2 mL of plasma will be stored at -80°C for future analysis.

Samples and data will be stored in a linked anonymised format. Samples will be labelled using a combination of study reference, unique study identifier and cross referenced with location code numbers to permit accurate linkage to study data and the consent form.

The master database will be held by the CI in a password encrypted file.

Where participants do not agree to the future use of the samples, they will be destroyed in accordance with the Human Tissue Act, 2004.

LABORATORY ANALYSES

Routine blood/laboratory tests will be analysed in a local NHS laboratory at the Royal Derby Hospital, which is serviced and managed according to national standards and governance frameworks. No DNA or RNA extraction will occur as part of this study. Assays for CML and inflammatory markers will be conducted in research laboratories at the University of Nottingham.

STATISTICS

Methods

Statistical analysis will be conducted by [name] (PhD student), [name] and [name]. Data management and statistical analyses will be performed using statistical software SPSS version 22.0.

Data will be presented as mean \pm standard deviation, median (percentiles 25%-75%), or percentages, as appropriate.

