Tolerability and safety of the nutritional support intervention during the proof of principle study (Study 2) will be assessed by direct interview. If any serious adverse event (SAE) is reported during the study, it will be recorded on an appropriate SAE report form.

Procedures for missing, unused and spurious data

All SAF measurements, biochemistry, nutritional and quality of life assessments for Study 1 and 2 will be used in the statistical analysis, including data from participants who did not complete the entire study protocol.

Definition of populations analysed

Study 1:

Full Analysis set: All participants included in the protocol for whom at least one post-baseline assessment of the primary endpoint is available.

Per protocol set: All participants in the Full Analysis set who are deemed to have no major protocol violations that could interfere with the objectives of the study.

Study 2:

Full Analysis set: All randomised participants, who participated in at least one treatment and for whom at least one post-baseline assessment of the primary endpoint is available.

Per protocol set: All participants in the Full Analysis set who are deemed to have no major protocol violations that could interfere with the objectives of the study.

ADVERSE EVENTS

The occurrence of an adverse event as a result of participation within this study is not expected and as such no adverse event data will be collected.

ETHICAL AND REGULATORY ASPECTS

ETHICS COMMITTEE AND REGULATORY APPROVALS

The study will not be initiated before the protocol, informed consent forms and participant information sheets have received approval / favourable opinion from the REC, and the respective NHS Research & Development (R&D) department. Should a protocol amendment be made that requires REC approval, the changes in the protocol will not be instituted until the amendment and revised informed consent forms and participant information sheets (if appropriate) have been reviewed and received approval / favourable opinion from the REC and R&D departments. A protocol amendment intended to eliminate an apparent immediate hazard to participants may be implemented immediately providing that the REC are notified as soon as possible and an approval is requested. Minor protocol amendments only for logistical or administrative changes may be implemented immediately; and the REC will be informed.

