Study conduct may be subject to systems audit of the Trial Master File for inclusion of essential documents; permissions to conduct the study; Trial Delegation Log; CVs of study staff and training received; local document control procedures; consent procedures and recruitment logs; adherence to procedures defined in the protocol (e.g. inclusion / exclusion criteria, correct randomisation, timeliness of visits); AE recording and reporting; accountability of study materials and equipment calibration logs.

The Study Coordinator/Academic Supervisor, or where required, a nominated designee of the Sponsor, shall carry out a site systems audit at least yearly and an audit report shall be made to the Trial Steering Committee.

TRIAL DATA

Monitoring of study data shall include confirmation of informed consent; source data verification; data storage and data transfer procedures; local quality control checks and procedures, back-up and disaster recovery of any local databases and validation of data manipulation. The Study Coordinator/Academic Supervisor, or where required, a nominated designee of the Sponsor, shall carry out monitoring of study data as an ongoing activity.

Entries on CRFs will be verified by inspection against the source data. A sample of CRFs (10% or as per the study risk assessment) will be checked on a regular basis for verification of all entries made. In addition, the subsequent capture of the data on the study database will be checked. Where corrections are required these will carry a full audit trail and justification.

Study data and evidence of monitoring and systems audits will be made available for inspection by REC as required.

RECORD RETENTION AND ARCHIVING

In compliance with the ICH/GCP guidelines, regulations and in accordance with the University of Nottingham Research Code of Conduct and Research Ethics, the Chief or local Principal Investigator will maintain all records and documents regarding the conduct of the study. These will be retained for at least 7 years or for longer if required. If the responsible investigator is no longer able to maintain the study records, a second person will be nominated to take over this responsibility.

The Trial Master File and study documents held by the CI on behalf of the Sponsor shall be finally archived at secure archive facilities at the University of Nottingham. This archive shall include all study databases and associated meta-data encryption codes.

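### The protocol plans a Study 2 safety interview and a serious adverse event form, then rules out collecting any adverse event data

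*Combined protocol and SAP*

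**What the plan says.** Under Assessment of safety, in the Statistics section, the protocol makes two commitments:

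- An interview in Study 2: "Tolerability and safety of the nutritional support intervention during the proof of principle study (Study 2) will be assessed by direct interview".
- A form for serious events: "If any serious adverse event (SAE) is reported during the study, it will be recorded on an appropriate SAE report form".

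The ADVERSE EVENTS section follows shortly after. It says that "an adverse event as a result of participation within this study is not expected and as such no adverse event data will be collected".

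Four other places bear on the point:

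- Safety endpoints, under Trial / Study Design: "There will not be any safety endpoints for these studies".
- Criteria for terminating the study: "The intervention in Study 2 is not expected to be associated with any adverse effects".
- TRIAL CONDUCT, which lists what an audit may cover, including "AE recording and reporting; accountability of study materials and equipment calibration logs".
- Case Report Forms, which makes the CRF the main data collection instrument. Its list of contents has no item for adverse events, SAEs or tolerability.

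**The concern.** An SAE is an adverse event, and an interview about safety produces adverse event data. Site staff who obey the ADVERSE EVENTS sentence have no reason to write down what the interview finds or to complete the SAE form. Staff who obey Assessment of safety breach the ADVERSE EVENTS sentence.

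What is at stake is what can be said about tolerability at the end of Study 2. If events are not recorded, an absence of reported problems may mean that none occurred or that none were noted, and the data could not separate the two. The sponsor also reserves the right to stop the study for safety reasons (Discontinuation of the Trial by the Sponsor), and the plan leaves unclear what safety information would inform that decision.

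**Working it through.** The protocol gives no figure to reproduce here. The check compares the texts and looks for any wording that would let both instructions stand.

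1. **Does the ADVERSE EVENTS sentence limit itself?** It has two parts. The first says that events arising from participation are not expected. The second, "is not expected and as such no adverse event data will be collected", draws the consequence. The reference to participation qualifies the expectation. The collection rule that follows has no qualifier: it does not separate serious from non-serious events, related from unrelated events, or Study 1 from Study 2.

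2. **Does Assessment of safety limit itself so that the two fit together?** The interview is confined to Study 2 and its stated purpose includes safety. The SAE sentence refers to the study as a whole. It comes directly after a sentence about Study 2 but does not repeat that restriction, so its scope is open.

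3. **Does another section reconcile them?**
   - *Safety endpoints* rules out safety endpoints. Data can be recorded without being an endpoint, so this does not settle the matter.
   - *Case Report Forms* gives the interview answers no stated place.
   - *TRIAL CONDUCT* presupposes that adverse events are recorded. This is weak evidence, because the same list includes correct randomisation although neither study is randomised.

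4. **Would other planned data fill the gap?**
   - Monthly blood tests in Study 2 capture biochemistry, not complaints or events.
   - Reasons for withdrawal are recorded on the CRF, but only for those who leave.
   - Morbidity appears among the Study 2 secondary endpoints under Trial / Study Design ("Association of SAF levels with morbidity, biochemical variables (haemoglobin, HbA1C, urea" opens that list). The Study 2 secondary endpoints in the Statistics section omit it, so it is not a settled source.
   - None of these holds the interview answers.

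5. **How many participants are concerned?**
   - Study 2: 40 planned.
   - Study 1, only if the SAE sentence covers it: 100 HD + 40 PD + up to 30 incident = up to 170 planned.
   - These are headcounts, not expected numbers of events. They should not be added together, because Study 2 runs alongside Study 1 in the same renal unit and the documents do not exclude overlap.

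**The case against.** The best defence is that the sentences can be read together. Events caused by participation are not expected, so no routine log is kept; if an SAE nevertheless comes to light, a form is completed. The conditional wording of the SAE sentence, the absence of safety endpoints and the expectation of no adverse effects all fit that reading. The intervention is described as essentially usual NHS dietetic care with extra supervision and supplements, no Study 2 objective concerns tolerability, and some interview answers, such as how acceptable the support was, need not be adverse event data.

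Part of this stands. The narrower reading is plausible for SAEs, few events may be expected, and the audit list looks like generic text. But the protocol nowhere states that reading, and it does not account for the interview, which is meant to assess safety as well as tolerability. Low expected risk affects how many events there will be, not which instruction staff should follow. The Study 1 headcount is conditional, because the position of the SAE sentence may mean that only Study 2 was intended.

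It is also fair to say that a contradiction can be resolved in more than one direction. Any single consistent rule would remove it. The rule proposed below keeps the procedures the protocol already plans.

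**Conclusion.** The concern holds. The protocol commits to a safety interview and an SAE form and then excludes the data they would generate, and nothing in the documents reconciles the two.

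The effect is limited. It falls on the Study 2 interview answers and reported SAEs, and on Study 1 SAEs only under the wider reading. It weakens any tolerability statement but touches no planned endpoint. The sample size and the primary SAF analyses are unaffected.

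The conclusion assumes that the ADVERSE EVENTS sentence would be applied as written. That interview answers would go unrecorded is an inference from that sentence and the CRF list; no text says so directly. The correction should be made, though it does not threaten the main results.

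**What to change.** Reconcile the two sections:

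- Reword the ADVERSE EVENTS sentence so that it excepts the Study 2 interview answers and reported SAEs.
- State under Assessment of safety whether the SAE sentence covers Study 2 only or Study 1 as well.
- Add there that the interview answers and SAEs are recorded and summarised descriptively, and add the matching item to the Case Report Forms list.

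The statement that there are no safety endpoints can stay. The audit item in TRIAL CONDUCT would then refer to defined records.

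The cost is a change of protocol wording, a short record page and one descriptive listing. The interview and the form are already planned, so no visit or test is added. The change must follow the amendment route in the Ethics Committee and Regulatory Approvals section; if it is judged to need ethics committee approval, it cannot take effect until that is given.
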